	RO2 – Developing a conceptual framework for the economic evaluation of home monitoring glaucoma. Data collection RO2 – Healthcare staff We will convene focus groups with staff directly involved in HES monitoring e.g. clinicians, nurses, and administrative staff. Focus groups will be guided by a semi-structured topic guide and conducted, by the I-TRAC Research Fellow and a facilitator, at 2 of the recruiting sites and will include a mixture of Consultant Ophthalmologists (n=3), nurses (n=3) and administrative staff (n=3).	
	Data collection R02 – Patients	

We will also ask patients' during the interviews in RO1 to complete a short questionnaire that will investigate if home monitoring would trigger NHS contacts beyond those expected from current routine glaucoma monitoring (e.g. by asking how many times they would have contacted HES). This information will be posted back to the Study Office and then be inputted into the study database by a member of the Study team.

All interviews and focus groups will be audio-recorded and transcribed verbatim. The external company who will be contracted to transcribe the interview transcripts has previously conducted work of this type for the University of Aberdeen (NJC Secreterial) and the necessary work order contracts are already in place.

Personal data will be retained on password protected University computers, supported by secure servers, which are held in locked offices and can be accessed by authorised personnel only. Paper copies of consent forms will be stored in locked tambour filing systems, which are held in locked offices and can be accessed by authorised personnel only. In accordance with HSRU code of conduct (and wider University of Aberdeen policies), all data will be password protected against unauthorised access and stored in accordance with data protection legislation. All participants will be assigned a unique identifier so as to allow anonymisation of data. All identifiable and non-identifiable data will be stored separately with paper copies being held in locked tambour units that only the research team have access to. Direct quotes may be used in the publication of research findings but these will not be attributed to named individuals and any identifiable information will be removed.

It is important to highlight that research activities may be conducted in person or remotely (through telephone or videoconferencing facilities) and this will depend on current social distancing regulations in place at the time of data collection.

3.2.	Data Management System

A bespoke study database will be developed by HSRU programmers , details		
below:		
Bespoke database utilising the following:		
Website: .Net 4.5 framework		
Database: SQL Server 2014		
Host Operating System: Windows Sever 2012 R2 (Virtual)		
Development Tools: C# in Visual Studio, .NET		
License: UOA		
Back-up and recovery procedures		
Databases are backed up onto hard disc at an offsite location. The		
programming team keep the last 5 nights backups to ensure timely response to		
any issues and for disaster recovery situations. After 5 days the backs ups are		
handled by IT Services in a normal rotation method.		
Data Query Rules / Validations		
Appropriate automated range checks and validation have been inbuilt to the		
database to ensure that, where possible, outlying values cannot be recorded.		
Details of any range checks and validation performed at time of data entry will		
be detailed within the testing documentation for CRF.		
An appropriate validation list for each CRF will contain the field name, the		
validation type, the values and any appropriate validation message.		
Query Handling		
Data will be monitored by the Research Fellow. Responsibilities include:		
Data will be monitored by the Research renow. Responsibilities include.		
Encuring data is optioned on the trial database in an appropriate timely		
 Ensuring data is entered on the trial database in an appropriate timely manner: 		
 Identifying missing data and contacting the sites to ensure data completion. 		
 Central monitoring will be undertaken throughout the trial by the TM. 		
It is the responsibility of the Descerch follow and the Statistician to ensure all		
It is the responsibility of the Research fellow and the Statistician to ensure all		
data queries are resolved before data is locked for analysis		
Quality Assurance		
Two forms of Audit logs exist, these logs capture all data keystrokes entered in		
the CRF; date, time and by whom will be recorded. Also, values added and		
changes to values will be recorded.		
Any significant data quality issues identified during the trial will be reported to		
either the Project Management Group who will investigate as appropriate.		
Security		
Usernames Each user will have a unique username and password.		
Roles		

The website application supports the concept of defined roles at a component level which may be configurable on a per study basis.

Login

The website application will disable an account after a specified number of incorrect logins, this is currently set at 3.

Participants will be assigned a unique identifier on their consent form. Consent forms and CRFs will be scanned at site and transferred to a secure area of the database. Hard copy consent forms will be stored securely in a locked filing cabinet at site for each patient in RO1 and all other hard copy consent forms and questionnaires stored at the study office. Field notes will be anonymised and not shared outside the research team. All electronic resources will be stored on the University of Aberdeen server, with access restricted to the study team.

4.	Statistics and Data Analysis
4.1.	Sample Size Calculation
	RO1 - Understand the views of patients and clinicians on whether digital technologies for glaucoma home monitoring would be feasible and acceptable.
	Patients A purposive sample of 45 patients (with varying disease severity informed by RO1) being monitored by HES for glaucoma in NHS hospitals in Belfast, Edinburgh and Nottingham will be invited to participate in using the home monitoring technology to measure their disease progression. The sample size of 45 is in line with previously proposed sample sizes of between 24 and 50 recommended to estimate standard deviations for future sample size calculations [34, 35]. Each of the three hospitals will aim to recruit 15 patients
	For the interviews, a purposive sample of patients will be selected based on site, age, gender and adherence levels (as per sampling for similar studies, an initial analysis sample of 10 patients will be conducted and a stopping criterion (when three further interviews have been conducted with no new themes emerging) defined to determine data saturation [36].
	Ophthalmologists Two focus groups with 6–8 ophthalmologists per group (samples deemed appropriate in this context) will be conducted.
	Researchers and NHS Staff Up to 6 members of relevant research teams will be invited to share their experience of delivering studies in this setting with a particular focus on the barriers and facilitators to design and delivery. We will aim for two members (Chief investigator and Trial Manager) of each of the trial teams will be interviewed (n=6). In addition, one Research and one IT person from each of the 3 Trusts will also be invited.
	RO2 – Developing a conceptual framework for the economic evaluation of home monitoring glaucoma. Healthcare staff Two focus groups with a mixture of Consultant Ophthalmologists (n=3), nurses (n=3) and administrative staff (n=3) per group (samples deemed appropriate
	in this context) will be conducted. Patients As per RO1 above.
4.2.	Proposed Analysis

RO1 - Understand the views of patients and clinicians on whether digital technologies for glaucoma home monitoring would be feasible and acceptable.

Patients

RO1 will collect qualitative data from interviews and focus groups and will also collect quantitative data through the weekly measurement using the home monitoring equipment. Two types of clinical outcome data will be collected: 1. Tonometry data; and 2. Perimetry data. The home tonometer measures intraocular pressure (IOP) and presents data on a scale of 0-70 (0 = low pressure, 70 = high pressure), with most patients measuring between 10-30. Visual field tests using the home perimeter present a mean deviation, which quantifies the severity of the visual field loss, presented on a scale of 0-30 (0 = no damage, 30 = very damaged). These clinical outcome data collected using the home perimetry (visual field, 0-30) and tonometry (IOP, 0-70) technology will be analysed using descriptive statistics to describe the patient sample and the changes (if any) in the measurements over time. We will also confirm that we are able to get repeated measures through home monitoring. The data collected using the home monitoring technology will be compared to the clinic visit measurements at 4 months to qualitatively assess the agreement between home and hospital-based monitoring. We will use Bland-Altman methodology to assess the limits of agreement between the two IOP measurements. An added feature of the data we are collecting is repeated measures of home IOP. There are several ways then to use the data. We will outline the full detail in a statistics analysis plan before the study commences, but in brief agreement comparisons of interest will be agreement between 4-month clinic IOP and:

- Mean IOP over period (using random effect models outline in Myles and Cui [37]
- Most recent home IOP measurement
- Highest IOP measurement.
- The other quantitative data collected in RO2 relates to recruitment rates, adherence to intervention (assessed by number of weekly measurements completed), and requirements for further training (assessed by additional training received: face-to-face or over telephone). These data will be analysed using descriptive statistics and presented as frequencies.

Interview data will be analysed using a Framework approach which will allow data to be coded both deductively (informed by the key constructs and domain from within the guiding theoretical frameworks) but also inductively, allowing identification of additional important themes to be identified. Constructs from the Theoretical Framework of Acceptability that will guide analysis include: affective attitude, burden; ethicality; intervention coherence; opportunity costs; perceived effectiveness; and self-efficacy. These will be supplemented with constructs from the Consolidated Framework for Intervention Research and include: intervention characteristics, outer setting, inner setting, characteristics of the individuals involved, and the process of implementation. Data will be compared and coded through a process of constant comparison to provide a summary of key points that interviewees consider important in this context. Preliminary analysis will run concurrently with data collection to allow the topic guide to evolve as necessary. Two researchers will code the first

three transcripts concurrently to develop a coding strategy, which will be informed by the theoretical frameworks (outlined above) and the inductive analysis. Subsequent transcripts will be coded by one researcher and a random 10% sample will be independently double coded. Data will be managed through NVivo.
Ophthalmologists This will be conducted as per plans outlined above for the patient interviews but adapted accordingly for focus on impacts to service.
Researchers and NHS Staff This will be conducted as per plans outlined above for the patient interviews but adapted accordingly to focus on researcher and service challenges and solutions to delivering large scale evaluations of home monitoring for eye disease.
RO2 – Developing a conceptual framework for the economic evaluation of home monitoring glaucoma. Healthcare staff Based on staff responses in the focus groups to service use, ranges of staff time and staff time savings will be estimated and valued using standard sources such as Curtis and Burns [39]. Descriptive statistics will be used to report the data collected on resource use (e.g. staff time). The clinical data will be analysed as stated previously – see RO1 data analysis.
Patients The interview data collected in RO1 will be analysed as reported previously using a Framework approach with attention being paid to the patient derived attributes important for informing glaucoma monitoring services. We will collect data on the number of contacts (hospital visits, phone calls or home visits) triggered by patients under home monitoring. Descriptive statistics will be used to analyse these data (i.e. mean, median, interquartile range, maximum and minimum values). These health care contacts will be subsequently valued using standard NHS unit cost sources [39].

es relating to the I-TRAC Study will be stored on the University's secure ork accessible only to those personnel with appropriate access rights as mined by the data owner in terms who has read/write access to a named or application. IT services implements access only when there is a written est from the data or application owner, or nominate depute if there is
he home monitoring applications, which are accessed via a secure ite, this is handled via roles tailoring access to data as appropriate for the f the user assigned to them by the researcher
ata will be processed on PCs connected to the University's network and ed within the Health Services Research Unit (HSRU). These require a login assword to be provided by the user. Access to University IT resources is cted to users who are approved and issued with a user name and yord. Password complexity is enforced.
ystem is maintained by the programming team and IT services at the rsity of Aberdeen who will also have responsibility for the physical ity of the system. IT services are responsible for the physical security of stitutional data centres and their contents. The data storage and servers to process the data are located in these data centres.
s to the web-based application is controlled by user name and password nly those personnel identified by the researcher as working on the I-TRAC will be allowed access to the website and appropriate data. New users asigned a strong password and advised they should change this to a yord of their choice. IT services require that all users agree to their Terms onditions of use. Confidentiality agreements are a matter for HR and the dual Colleges. All staff agree, as part of their terms and conditions of oyment, to abide by the University's Information Security Policy. HSRU's cting Information Policy is given to all new members of staff. All prised users are fully trained in Good Clinical Practice.
by data required to be sent between sites, all files will be securely encrypted cansferred using ZendTo. All files uploaded and temporarily stored on ZendTo e held on equipment owned and operated at the University of Aberdeen Data e. All data will be subject to the Data Protection regulations and laws. ZendTo no way a "cloud" service. Everything will be stored (even temporarily) on ment directly owned by the University of Aberdeen, and managed by its own of. All access to data will be very tightly and strictly controlled. All accesses to on ZendTo will be logged. Furthermore, uploaded data will be only held on "o for a maximum of 14 days, after which time it will be automatically deleted. is no "undelete" facility available at all. No backups will be taken of the ded data. After an uploaded file has been deleted, there is no way of ering the file.
y Management and Oversight Arrangements

		Charles Management Cream	
	5.1.	L. Study Management Group	
		The study will be co-ordinated by a Study Management Group, consisting of the	
		grant holder (CI), external PIs, co-applicants, and Research Fellow.	
	5.2.	Study Management	
		A Research Fellow will oversee the study and will be accountable to the CI. The Research Fellow will be responsible for checking the CRFs, questionnaires, and other data collection forms for completeness, plausibility and consistency. However, this remains the overall responsibility of the CI. Any queries will be resolved by the CI or delegated member of the study team.	
		A study-specific Delegation Log will be prepared for each site, detailing the responsibilities of each member of staff working on the study.	
	5.3.	Study Steering Committee	
		An independent Study Steering Committee (SSC) will be established to oversee the conduct and progress of the study as per the recommendations from the funder. The terms of reference of the SSC, the draft template for reporting are detailed in Appendix 1.	
	5.4.	Data Monitoring Committee	
		An independent Data Monitoring Committee (DMC) is not required for this study as confirmed by the funder.	
6.		Inspection of Records	
	12.1	The CI, PIs and all institutions involved in the study shall permit study related monitoring, audits, and REC review. The CI agrees to allow the Sponsor or, representatives of the Sponsor, direct access to all study records and source documentation.	
7.		Good Research Practice	
	7.1.	Ethical Conduct of the Study	
		The study will be conducted in accordance with the principles of good clinical practice (GCP).	
	7.	practice (GCP). In addition to Sponsorship approval, a favorable ethical opinion has been obtained from the appropriate REC (Ref id: 20/EM/0244) and appropriate NHS R&D approval(s) will be obtained prior to commencement of the study.	

	access to study staff only. The CI and study staff involved with this study will not disclose or use for any
	purpose other than performance of the study, any data, record, or other unpublished, confidential information disclosed to those individuals for the purpose of the study. Prior written agreement from the Sponsor or its designee will be obtained for the disclosure of any said confidential information to other parties.
	Participants involved in the interviews or focus groups will be assigned a pseudonym/study code on their consent form. We will keep consent forms securely in a locked filing cabinet. Any field notes will use the same pseudonym/study code and this will not be shared out with the study team. All audio-recordings and transcripts will be anonymised to ensure confidentiality.
7	Data Protection
	The study team involved with this project will comply with the requirements of the General Data Protection Regulations (GDPR) and the Data Protection Act 2018. The HRA recommended wording to fulfil transparency requirements under the GDPR for health and care research has been included in the PIS.
	The CI and study staff will also adhere, if appropriate, to the current version of the NHS Scotland Code of Practice on Protecting Patient Confidentiality. Access to collated participant data will be restricted to the CI and appropriate study staff.
	Computers used to collate the data will have limited access measures via user names and passwords.
	Published results will not contain any personal data that could allow identification of individual participants.
7	Insurance and Indemnity
	The University of Aberdeen is sponsoring the study.
	Insurance –
	• The University of Aberdeen will obtain and hold a policy of Public Liability Insurance for legal liabilities arising from the study.
	Indemnity: The Sponsor does not provide study participants with indemnity in relation to participation in the Study but has insurance for legal liability as described above.
	Study Conduct Responsibilities

8.1.	Protocol Amendments, Deviations and Breaches	
	The CI will seek approval for any amendments to the Protocol or other study documents from the Sponsor (in the first instance), REC and NHS R&D Office(s). Amendments to the protocol or other study documents will not be implemented without these approvals.	
	In the event that a CI needs to deviate from the protocol, the nature of and reasons for the deviation will be recorded in the CRF, documented and submitted to the Sponsor. If this necessitates a subsequent protocol amendment, this will be submitted to the Sponsor for approval and then to the appropriate REC and lead NHS R&D Office for review and approval.	
	In the event that a serious breach of GCP is suspected, this will be reported to the Sponsor immediately using the form "Breach Report Form".	
8.2.	Study Record Retention	
	Archiving of study documents will be retained for 10 years after study end date in line with the Sponsor's archiving SOP.	
8.3.	End of Study	
	The end of study is defined as completion of data analysis and study reporting. The Sponsor, CI and/or the SSC have the right at any time to terminate the study for clinical or administrative reasons	
	The end of the study will be reported to the Sponsor and REC within 90 days, or 15 days if the study is terminated prematurely. The CI will ensure that any appropriate follow up is arranged for all participants.	
	A summary report of the study will be provided to the Sponsor and REC within 1 year of the end of the study.	
9.	Reporting, Publication and Notification of Results	
9.1.	Authorship Policy	
	Ownership of the data arising from this study resides with the study team and their respective employers. On completion of the study, the study data will be analyzed and tabulated, and a study report will be prepared. See Appendix 5.	
9.2.	Publication	
	The study report will be used for publication and presentation at scientific meetings. Investigators have the right to publish orally or in writing the results of the study.	
	Summaries of results will also be made available to Investigators for dissemination within their clinical areas (where appropriate and according to their discretion).	

9.3.	Peer Review
	This study has been externally peer reviewed as part of the National Institute for Health Research funding process and a cope of these reviews, and our responses, will be submitted as part of the application.
10.	Patient Public Involvement
	Research to 'improve early diagnosis of sight-threatening glaucoma' is a top priority (for patients and clinicians) for funding (JLA PSP). Therefore, patients have been directly involved in identifying and prioritising this research question. We have worked closely with [name], user of the glaucoma service, who has agreed that this is an important research question and is willing to act as PPI coapplicant and member of the study steering committee. [name] has provided input into the overall plan of activities. However, [name] was unable to complete the activities required on the online MIS form due to being out of the country but had confirmed she was happy to continue to contribute. We will identify at least one other PPI partner to contribute to the study going forward. There will be ongoing PPI input in the design and piloting of all aspects of the study. In particular, guidance during the preparation of all patient facing documentation will be particularly important, for example, on the information leaflets but also critical input to the topic guides for interviews will be key and co-production of the study results to participants. The International Glaucoma Association (UK-based charity to support people with glaucoma) will act as advisors across the project.

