	The eye measurement data captured using the home monitoring devices will only be assessed at the end of the study. Therefore, there will be no opportunity to identify incidental or abnormal findings. However, we are not deviating from best practice as NICE recommendations suggest patients be monitored every 6- 12 months. The final I-TRAC eye measurement will occur in hospital at 4 months after baseline, already more frequent than standard clinical care, and any change in disease progression will be treated accordingly. It is also worth noting that glaucoma has a slow rate of progression so it is unlikely that an abnormal result will be identified even within the 4 months. The purpose of the I-TRAC study is feasibility and acceptability of monitoring to patients and HCPs, not accuracy of measurement, hence why measurement data will not be reviewed in real time.
	Safety information on devices The perimetry assessment, the Melbourne Rapid Field (MRF) is the only home perimeter currently available in an online application, there are several studies confirming its reliability, and is the only home perimetry test that has been evaluated in a longitudinal cohort of patients. It is currently being used in another research Study run in Moorefields Hospital, London. Glance Optical, the developers of the MRF, will provide advice, free software downloads for 15 units, technical operating support. Glance Optical have agreed to use a University of Aberdeen template agreement to agree the terms of use of the MRF. The agreement will not include any obligations for the University to share study data with Glance Optical.
	Regarding home tonometry, icare HOME is CE marked and is the only device currently available in the UK. The icare HOME technology is used by some clinicians in the UK as part of routine clinical care, although we don't know how common is its use or which patients it is used with and what they think of it. Mainline instruments are the UK distributor for the icare HOME rebound self-tonometer. The University have agreed a discounted rate for the device and this purchase will be made under Mainline Instrument's standard terms of purchase. These purchase terms do not include any obligations for the University to share study data with Mainline Instruments.
2	Data Callestian and Management
3.	Data Collection and Management
3.1.	Data Collection

/112020		
	RO1 - Understand the views of patients and clinicians on whether digital	

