Appendix 4: Study Matrix

Participants	Study Processes				
Research Objective	nderstand the views of patients and clinicians on whether digital technologies for glaucoma home				
monitoring would be feasible and acceptable					
	Data collection	Timing and frequency			
Patients	 45 patients will: Have a baseline study visit in HES clinic where demographic data ((e.g. age, gender, education, disease status, previous eye treatments) will be collected from the medical notes and visual field test and IOP will be taken. Be asked to take measurements (IOP with the home tonometer and visual field with the home perimeter) at home using the home tonometer and the perimeter. Data will be stored within the visioninhome.uk website and downloaded to the study website . Patients who require additional training on the technology will be offered opt-in refresher training at a return clinic visit (within 1 month of baseline). Have end of study visit in HES clinic for final visual field test and IOP and also a short resource use questionnaire 	 Baseline data collection and training on home monitoring equipment to last 90 mins (60 mins of which is standard care and 30 minutes is the research activity). Baseline eye measurement may be provided from home monitoring equipment if not able to attend HES. Patients will be asked to use the equipment every week for 4 months. Perimetry measurement take approximately 15 minutes Tonometer measurement takes approximately 5 minutes Final eye measurements at 4 months – approx. 30 mins – and participant completed questionnaire – approx. 10 minutes. May be provided from home monitoring equipment if 			
	interviews to explore acceptability of home monitoring generally and focus on the requirements (both in the	not able to attend HES.			
	short, medium, and long term) of the digital technologies				

	under investigation. Interviews will take place within the clinic at the time of the final visual field and IOP assessment	 Interviews will be conducted once after patients have completed the 4-month home monitoring measurements. Interviews are anticipated to last between 45-60 minutes. Interviews will be done either face to face in clinic or via video/audio call if necessary.

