Appendix 6: COVID-19 Contingency Plan

This appendix outlines aspects of study design and conduct that would have to change for the I-TRAC research study should COVID-19 cause restrictions on research at any point during the study timeline. The potential changes to process required are presented below for each of the Research Objectives and the associated participants.

RO1 - Understand the views of patients and clinicians on whether digital technologies for glaucoma home monitoring would be feasible and acceptable.

Patients

Consenting participants

Patients will be sent an invitation letter, information sheet and consent form in the post. Research nurses (appropriately GCP trained) will then telephone the patients to provide an opportunity to ask any questions they have and seek verbal consent. They will then arrange a time convenient for the patient to introduce them to the home monitoring equipment and be trained in its use. The research nurse will then arrange for the patient to be sent the home monitoring equipment and provide instruction on how to return it at 4 months.

For participants who agree to be interviewed, verbal consent will be reconfirmed by the I-TRAC Research Fellow who will be appropriately trained in GCP before the interview commences.

If a participant does not wish to be recorded for any of these steps, we will arrange for an independent witness to observe the consent process. The witness and the researcher will complete the verbal consent script annexe to document that consent was given.

Data collection

Once consented, patients will be trained by the research nurses in how to conduct the measurements using the home monitoring equipment over MS Teams. Visual field and intra-ocular pressure data will be obtained from patient. If this has to be done remotely (via MS Teams), patients will be asked for the readings from the home monitoring equipment. This process will also be followed for the 4 month end of study measurement should the patient not be able to attend HES in person.

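### Section 2 relies on a 4-month hospital check that patients on the remote route may not have, and no procedure covers an abnormal home reading reported on that route

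*Protocol*

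**What the plan says.** All references are to the second protocol (Work Packages 2-4).

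Section 2 (Study and Safety Assessments) states: "The eye measurement data captured using the home monitoring devices will only be assessed at the end of the study". It draws the consequence: "Therefore, there will be no opportunity to identify incidental or abnormal findings". In support it says that "The final I-TRAC eye measurement will occur in hospital at 4 months after baseline, already more frequent than standard clinical care", and that any change found will be acted on. It gives no exception to the hospital measurement. It also cites the 6 to 12 month monitoring interval recommended by NICE, the slow course of glaucoma, and the study's focus on feasibility rather than accuracy. Section 3.1 likewise places the baseline and 4-month measurements in clinic.

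Appendix 4 (Study Matrix) lists the end-of-study visit as "Have end of study visit in HES clinic for final visual field test and IOP", but its timing column adds: "Baseline eye measurement may be provided from home monitoring equipment if not able to attend HES". The entry for the final measurement carries the same allowance, although its sentence is broken across table cells in the text available.

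Appendix 6 (COVID-19 Contingency Plan) says that, when measurement is remote, "patients will be asked for the readings from the home monitoring equipment" over MS Teams. It continues: "This process will also be followed for the 4 month end of study measurement should the patient not be able to attend HES" in person. The values go on a case report form, and the research nurse conducts the end-of-study call.

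Section 4.2 states: "The data collected using the home monitoring technology will be compared to the clinic visit measurements at 4 months". It names the 4-month clinic intraocular pressure (IOP) as the reference in three agreement comparisons.

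**The concern.** Section 2 explains why it is acceptable that nobody looks at home readings as they arrive. Two of its statements are factual: a hospital measurement follows at 4 months, and staff have no means of noticing an abnormal home value. The remote route in the appendices makes the first untrue for the patients who use it at 4 months. It makes the second untrue at least at baseline, when a member of the study team asks for the reading and writes it down.

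At stake is what happens when a patient reports a raised pressure on such a call. Section 16.1 says treatment is escalated when pressure exceeds the individual target. The staff member who hears such a value has only a procedure that says it cannot be seen. Slow progression does not settle this, because a pressure above target can show in a single reading, including the first.

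**Working it through.** No sample size, power or error rate is involved, so the check is a comparison of the texts.

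| Question | Sections 2 and 3.1 | Appendices 4 and 6 (patient cannot attend HES) |
|---|---|---|
| Where is baseline measured? | In clinic | Home device |
| Where is the 4-month measurement made? | In hospital | Home device |
| Do staff learn home readings during the study? | No; data are assessed at the end | Yes; they are asked for on the call and recorded |
| What happens with an abnormal home reading? | Treated as not identifiable | Nothing stated |
| Is a later hospital measurement required? | Not needed | Not stated |

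**Hospital study measurements per patient.** Sections 2 and 3.1 imply 2. With one measurement taken remotely, 2 - 1 = 1. With both taken remotely, 2 - 2 = 0. The appendices therefore allow a patient to finish with no hospital study measurement.

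**Baseline.** A home reading reported on the remote baseline call reaches staff about 4 months before that patient's final measurement. This conflicts directly with the statement that home data are assessed only at the end and offer no opportunity to find anything abnormal.

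**Four months.** This reading comes at the patient's own end of follow-up, so the conflict with end-of-study assessment is weaker. The main problem is that the hospital measurement section 2 relies on has not taken place.

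**Who hears the reading.** Appendix 6 puts this sentence in the passive. The research nurse delivers the remote training and runs the 4-month call, so it is a fair inference, not a stated fact, that the nurse receives the values. That some member of study staff does so follows from the text.

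**Does Appendix 6 adjust section 2?** It sets out what would have to change under restrictions, covering consent, training, data collection, interviews and oversight. The abnormal-findings procedure is not among the changes.

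**Number affected.** The protocol gives no count or forecast of remote patients. The range is 0 to 45. At no more than two sets of readings each, the upper bound is 2 x 45 = 90 sets.

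**The case against.** The strongest reply is that this is a default and a contingency, not a contradiction. Appendix 6 is meant to displace the main text, and both the Summary and section 3.1 warn that activities may be remote, depending on distancing rules. Appendix 4's allowance may be the same contingency, although it is not worded that way. This explains why the two routes differ. It does not supply the missing step, because the displacing text leaves the abnormal-findings procedure untouched.

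The reply is right about the limits of the safety effect. Patients are recruited from those already under treatment at the three sites (section 19.2), self-referral back to HES is anticipated (section 18.1), and section 8.3 makes the Chief Investigator responsible for appropriate follow-up. No passage suspends routine review.

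Three stronger readings are tempting, and the documents do not support them:

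- A reader might infer that remote patients go unchecked for longer than usual care allows. The protocol does not say when each patient's routine interval starts, so no added delay can be calculated.
- A reader might take the published disagreement between the home tonometer and Goldmann tonometry (section 18.1) as a rate of missed abnormal pressure. It measures agreement between devices, not harm.
- A reader might infer that home readings will be compared with themselves, making the limits of agreement too narrow. Section 4.2 names a clinic measurement as the reference and leaves the detail to a statistical analysis plan. Nowhere is a home reading said to stand in as clinic IOP.

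**Conclusion.** The point holds in a limited form. For any patient measured remotely at 4 months, the hospital check offered in section 2 as support for not reviewing home readings is absent. For any patient measured remotely at baseline, the claim that abnormal findings cannot be identified is untrue. On either call, a reported abnormal value has no stated action.

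The loss is one extra study check per patient at 4 months, on top of routine HES care. Section 2's other arguments, the recommended monitoring interval and slow progression, are unaffected. The size cannot be narrowed beyond 0 to 45 patients. If everyone attends in person, the problem never arises. The conclusion assumes only that the remote route is used for at least one patient and that the person on the call takes in what is reported.

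**What to change.** 1. In section 2, state that the 4-month hospital measurement applies unless the remote route in Appendices 4 and 6 is used.
2. Replace the sentence on having no opportunity to find abnormal results with: *Home readings are not reviewed in real time, except those reported on a remote baseline or 4-month call. These IOP and visual field readings are passed to the site ophthalmologist, who arranges HES review if IOP is above the patient's target or the visual field has worsened.*
3. In Appendices 4 and 6, record remotely reported values as home readings, so that they are never used as the 4-month clinic IOP in section 4.2.

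Rebooking a missed hospital measurement should be optional, where feasible. It would restore the check, but it adds a visit for remote patients.

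The cost is an amendment under section 8.1. The site ophthalmologists look at no more than two sets of readings per remote patient, so at most 90 sets if all 45 are remote. The agreement analysis may include fewer patients, because those without a hospital measurement have no clinic reference.
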